7.2.3 Final Visit: WCV #3

At WCV #3 (T₆: Day 730 ± 90)

Before Provider Encounter in the Exam Room

- If a parent/caregiver will be asked to complete the COVID-19 questionnaire, they will be re-consented with the updated consent form (12/7/20).
- Parent/caregivers will complete the following self-administered questionnaires: A1: Illness Perception Questionnaire-Revised for Dental (IPQ-RD) and A2: Parent Questionnaire, COVID-19 Dental Visit Questionnaire (if applicable)
- Dental hygienist will perform child dental screening examination and study staff will record results of the dental screening examination. Results will not be available to the provider unless the hygienist finds that the child has urgent needs that requires immediate attention

During Provider Encounter in the Exam Room

- Caregivers attending WCV's will receive OH information, prescription to take the child to the dentist + list of local Medicaid-accepting dentists, based on study arm.
- Caregivers attending WCV's may have study staff audiotape or directly observe the provider encounter to evaluate the provider's delivery of OH communication (for a sample of visits).

After Provider Encounter in the Exam Room/Waiting Area

- Caregivers will provide feedback about the OH information given to them during the medical visit using a short self-administered exit questionnaire (A3). Actively enrolled parents will also complete a short (7 item) COVID-19 Questionnaire which asks if they have altered their behavior related to taking their child to the dentist due to the COVID19 pandemic.

7.2.4 Parent/Caregiver and Child Withdrawal Visit

The following procedures will be followed for participants who choose to withdraw early or whose participation is terminated by the PI:

- Personal contact (by phone or in-person) by study staff will be made to confirm withdrawal.
- Record any adverse event reported by participant.
- Debrief about the interventions.
- Obtain responses to the study questionnaires (if applicable)

- If a parent/caregiver and child withdraws or changes to a practice not participating, visits and data collection will end with these participants being considered lost to follow-up. Data collected up to the point of withdrawal will be used for analysis.

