Population:	Study participants: Pediatricians/Nurse Practitioners (n = 67) and child and parent/caregiver dyads (n = 1024) will be recruited from 18 primary care practices with $\geq 20\%$ Medicaid eligible children. Practices are selected from Rainbow Care Connection (RCC), a pediatric Medicaid accountable care organization that is part of the Rainbow Research Network (Clinical and Translational Science Collaborative [CTSC] supported practice-based pediatric research network), University Hospitals Cleveland Medical Center. The recruited practices have 60 pediatricians and 7 nurse practitioners who are 73% female and 27% male. We expect child and parent/caregiver demographics to be similar to Census and Medicaid data from northeast Ohio where Medicaid-enrolled children are 61% African American, 32% Caucasian, 5% Hispanic, and 2% other.
Phase:	Phase III
Number of Sites:	18 primary care practice sites
Description of Intervention:	The bundled intervention will impact providers, the practice and the parent/caregiver. The Common-Sense Model of Self-Regulation (CSM)-based education and skills training for the pediatrician or nurse practitioner are designed to educate them regarding chronicity of caries and teach them how to communicate core oral health facts to the parent/caregiver, provide a prescription to take the child to the dentist together with a list of area dentists who accept Medicaid, and document oral health in the EMR. The parent/caregiver will receive the CSM-based facts from the providers and should take their child to the dentist and improve oral health behaviors in the home. The practice level intervention will be enhancements to the EMR system to include oral health status for quality improvement of records and to use for follow-up with the parent/caregiver at subsequent wellchild visits.
Study Duration:	Approximately 36 months
Subject Participation Duration:	Parent/Caregiver = 24 months or completion of 3 WCV's Providers = 24 months or completion of 3 consecutive WCV's of enrolled patients. Additionally, all providers will complete a follow-up structured interview and debriefing session.
Estimated Time to Complete Enrollment:	9 months
Schematic of Study Design:	

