3.2.1 Primary Outcome Measures

The primary outcome will be dental attendance (receipt of dental care as yes/no, and number of visits). The primary outcome will be determined through a hierarchical process where Medicaid dental claims data (Current Dental Terminology (CDT) codes for preventive or restorative procedures in the past 12 months) would be the primary measure, followed by assessments through clinical dental screenings (restoration or extraction between WCVs #1 and #2, and between WCVs #2 and #3), conducted by calibrated examiners (See Section 14.2).

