5 STUDY ENROLLMENT AND WITHDRAWAL

5.1 Subject Inclusion Criteria

In order to be eligible to participate in this study, all of the following criteria must be met:

Practices:

- Use Electronic Medical Record (EMR)
- Have \geq 20% of pediatric patients covered by Medicaid Providers:
- Pediatrician or Nurse Practitioner with a minimum of 2 patient-care days per week
- Provide signed and dated consent form Parents or caregivers:
- Legal guardianship of Medicaid-enrolled children aged 3-6 years attending well-child visit (WCV)
 - Must be \geq 18 years
 - Speak English or Spanish
 - Provide signed and dated consent form
 - Planning to stay in the immediate area (both parent/caregiver and child) for at least two years Child:
 - Ages 3-6 years
 - Enrolled in Medicaid

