5.5.2 Handling of Subject Withdrawals or Subject Discontinuation of Study Intervention

All reasons for dropout/withdrawal or discontinuation of the study intervention will be documented in the tracking database and reviewed by the study team and reported to the NIDCR Medical Monitor and DSMB. For gathering information on discontinuation, study staff will be contacting subjects at several time points. Study staff will contact parent/caregivers within 2 weeks of WCVs #1 and #2 to collect B1 questionnaires not previously returned, 6 months after WCVs #1 and #2 to complete B2 questionnaires, and 3 months and 2 weeks before WCVs #2 and #3 to remind caregivers to schedule/attend WCV.

In the event of a subject telling study staff that he/she is dropping out of the study, the study staff should gather the following information as much as the participant allows.

- Record the reason for dropping out of the study.
- Record any adverse event reported by the subject.

- Complete the appropriate questionnaire nearest the drop out time point.

If it is determined by study staff that a participant should be discontinued from the study, the decision to withdraw a participant must be discussed and confirmed by the PI.

Caregiver/child dyads that withdraw during the baseline (T_0) data collection window will be replaced by recruitment of additional parent/child dyads to reach enrollment goals.

Caregiver/child dyads that withdraw or that are lost to follow-up any time after the baseline data collection window will not be replaced, but data collected up to the point of withdrawal will be used for analysis.

Providers that withdraw after receiving the study intervention will not be replaced. See Section 7.1.4.

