7.1.4 Provider Withdrawal Visit

The following procedures will be followed for providers who choose to withdraw early or whose participation is terminated by the PI:

- Personal contact (by phone or in-person) by study staff will be made to confirm withdrawal.
- Debrief about the interventions.
- If a provider withdraws from the study and their patients are participants who see another provider at that practice, visits and data collection will continue. If the patient also withdraws by changing practices *to a non-participating practice*, visits and data collection will end with these participants being considered lost to follow-up. Data collected up to the point of withdrawal will be used for analysis.

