7.2.5 Parent/Caregiver and Child Unscheduled/Missed Visit

Unscheduled visits for parent/caregiver and child may occur if an enrolled child could not complete the oral health portion during the WCV. But, this is unlikely to happen due to the short amount time required for the oral health activities. Another possibility would be if a child is scheduled by the practice for a well child visit much sooner or later than the visit window. In these cases, study data would be collected per guidelines outlined in the MOP, but the time length between visits will be accounted for in the analysis stage.

Other instances of unscheduled visits at follow-up, i.e. WCV2 or WCV3, may occur if a well child visit is missed by project staff (for example, a child comes in for a sick visit near the time a well child visit is due and the provider completes the well visit also) or another non-participating provider at the practice is scheduled to see the child for a well child visit. In these cases, the ICDAS, A2, A3 and B1 questionnaires will be completed when possible, either in person, by mail or through a link sent via text or e-mail to the parent/caregiver. The B2 follow-up will be completed as planned. In extreme situations, if we have missed the WCV2 or WCV3 and the child is scheduled to come in to see the enrolled provider for follow-up for a problematic issue within 3 months of the missed well child visit, we will arrange to complete the study visit at the follow-up visit. This determination will be made on a case-by-case basis. Arrangements will be made to have the parent/caregiver bring the child to the Dental Research Building for completion of the ICDAS dental screening. Also, due to scheduling irregularities in the part of the parent/caregiver, every child may not be scheduled for an annual WCV. In cases such as this, the parent/caregiver-child dyad may remain enrolled in the study and be seen for completion of 3 consecutive WCV's regardless of their timing. The time length between visits will be accounted for in the analysis stage.

COVID-19 Visits

Visits missed due to the COVID-19 pandemic will follow the protocol outlined above for unscheduled/missed visits.

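### A change to a non-participating practice ends all data collection, Medicaid claims included, so children who move may drop out of a primary analysis labelled intent-to-treat

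*Combined protocol and SAP*

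**What the plan says.** - **Source of the primary outcome (3.2.1).** Dental attendance is determined by a hierarchy in which "Medicaid dental claims data (Current Dental Terminology (CDT) codes for preventive or restorative procedures in the past 12 months) would be the primary measure". Clinical screening comes second and looks for "restoration or extraction between WCVs #1 and #2, and between WCVs #2 and #3". Section 8.1.1 has study staff abstract the claims.
- **Stop rule (7.2.4).** If a family withdraws or "changes to a practice not participating, visits and data collection will end with these participants being considered lost to follow-up". Data gathered before that point are kept. Section 7.1.4 has the same rule for a child whose provider has withdrawn, and words the move itself as a withdrawal: "If the patient also withdraws by changing practices".
- **Replacement (5.5.2).** Dyads who withdraw or are "lost to follow-up any time after the baseline data collection window will not be replaced".
- **Eligibility (5.1).** Caregivers must be "Planning to stay in the immediate area (both parent/caregiver and child) for at least two years".
- **Analysis (12.2 and 12.4).** The primary score is 0, 1 or 2: the number of follow-up years with a dental visit. The analysis is called intent-to-treat but is limited to participants with the required measurements. Missing attendance in either year is handled by sensitivity analyses that impute in favour of the null.
- **Claims access.** The protocol summary says that the practices belong to "a pediatric Medicaid accountable care organization". No section says how claims are obtained, or whether access continues after a child leaves a practice.

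**The concern.** The rule treats two different events alike. A family that withdraws consent has asked for data collection to stop. A family that changes pediatrician has not, and its child may still be enrolled in Medicaid and still generating the dental claims on which the primary outcome mainly rests. Stopping claims abstraction for such a child creates missing primary data through an event after randomization.

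That matters because leaving an Arm A practice also ends further exposure to the intervention. If movers are dropped, the comparison drifts from all enrolled children towards those who stayed and had the later contacts. The stop is also out of step with 7.2.5, which goes to some trouble to retain data through mailed or linked questionnaires, off-schedule visits and screening at another building.

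**Working it through.** **1. The plan's own figure.** Inputs from 12.2: 0.46 against 0.30, two-sided 0.05 pooled z test, ICC 0.04, 25% drop-out, 9 practices and 512 children per arm.
- Analysed per arm: 512 × 0.75 = 384, or 384 / 9 = 42.7 per practice.
- Design effect: 1 + (42.7 − 1) × 0.04 = 2.67. Effective n: 384 / 2.67 = 144 per arm.
- Power: 80.2%, against 80% stated. Solving in the other direction gives 378.7 analysed and 378.7 / 0.75 = 505 recruited per arm, against 512.

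The sample size reproduces, so this is not an arithmetic point.

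**2. Ceiling on any gain in power.** With no loss from any cause: 512 / 9 = 56.9 per practice, design effect 1 + 55.9 × 0.04 = 3.24, effective n 158.2, power 83.8%. The gain is 83.8 − 80.2 = 3.6 points. Retaining movers removes only part of the loss, so their share of this is smaller.

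**3. What happens to a mover.** A child attends WCV #1, receives the first contact, and later changes to a non-participating practice. Under 7.2.4 abstraction stops. Attendance already recorded is kept. Any part of the two years after departure is unobserved, so the score is incomplete unless earlier data already settle both years. The child is not replaced (5.5.2) and may not meet the inclusion condition in 12.4. The null-favouring imputation would bring the child back only in a sensitivity analysis. The multiple imputation in 12.4 is written for repeated-measures analyses, and the text does not say whether it reaches the primary score.

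**4. Illustrative shift.** The documents give no mover share, so these are assumptions: mover share s; stayers at the planned 0.46 and 0.30; Arm B movers at 0.30; Arm A movers at p. On the plan's binary scale, the all-enrolled difference is (1 − s) × 0.46 + s × p − 0.30.

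| s (children per arm) | p = 0.30, no effect kept | p = 0.38, half kept | p = 0.46, all kept |
|---|---|---|---|
| 5% (25.6) | 0.152 | 0.156 | 0.160 |
| 10% (51.2) | 0.144 | 0.152 | 0.160 |

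For example, 0.95 × 0.46 + 0.05 × 0.30 − 0.30 = 0.152. Against 0.160 in stayers the shift runs from 0 to 0.016. The no-effect column is an extreme bound, because every mover has had the WCV #1 contact. The primary model is proportional odds on 0/1/2, so the table shows scale only.

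**5. Year boundaries (secondary).** Claims look back 12 months with no reference date in the text, while screening runs from one WCV to the next. WCV #2 falls on days 275 to 455 and WCV #3 on days 640 to 820. WCV-to-WCV periods can therefore last 275 to 455 days and then 640 − 455 = 185 to 820 − 275 = 545 days. Section 7.2.5 says that "the time length between visits will be accounted for in the analysis stage", but the primary model described in 12.4 names no term for it.

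**The case against.** The strongest reply is about access. If claims reach the study through the accountable care organization, they may be out of reach once a child leaves, and 7.2.4 would then record an operational limit. The documents do not settle this. A reader might infer that the plan discards data it could certainly obtain, and the text does not support that. The point stands, because the protocol gives no such reason and applies a blanket stop, but the remedy must depend on access and consent.

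The plan also has safeguards. It allows for 25% drop-out, plans null-favouring sensitivity analyses, records reasons for drop-out, and enrols families who intend to stay in the area. These limit the harm. They do not recover an outcome that may be obtainable, and the residence criterion does not prevent a change of pediatrician within the area. It is also fair that a child leaving after WCV #2 misses only the WCV #3 contact, at the end of follow-up.

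On the years, a reader might infer that they are undefined, or that visits will be counted twice. That goes too far. Appendix E (the claims abstraction form) and the MOP were not available and may set the dates, 7.2.5 promises an adjustment for spacing, and no changed result has been shown.

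**Conclusion.** The point holds as an avoidable source of missing primary data after randomization. Sections 7.1.4 and 7.2.4 stop claims abstraction for children who have only changed practice, and 12.4 may then omit them from an analysis labelled intent-to-treat. The direction is towards an estimate for stayers. The size is unknown and probably small: 0 to 0.016 on a difference of 0.160 under assumed mover shares of 5% and 10%, and well under 3.6 points of power. It would be wrong to read this as a material bias or a power problem, since neither the mover share nor movers' attendance is given and no stated figure is in error. The conclusion rests on claims remaining reachable for at least some movers, which the documents leave open. The year boundaries are a secondary request for wording and not a stand-alone defect.

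**What to change.** Amend 7.1.4 and 7.2.4 so that a change to a non-participating practice ends study visits only. Claims abstraction should continue to the end of the two-year follow-up unless consent is withdrawn, provided the study's claims access and consent cover children who have left. If they do not, state that in the protocol and report the number of movers by arm.

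The cost is protocol wording, a check of claims access and consent, and some extra abstraction. No visits or participants are added. Gaps in Medicaid enrolment would remain.

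As a wording point, state in 3.2.1 and 12.4 when attendance years 1 and 2 begin and end, taking the dates from Appendix E or the MOP if they are set there, and say how the spacing adjustment enters the primary model. Fixed days from WCV #1 (1 to 365 and 366 to 730) are one option. They apply to every child whatever the visit dates, but when WCV #2 falls on day 455, the first 90 days of year 2 (90 / 365 = 25%) precede the second contact. WCV-to-WCV intervals are also legitimate if their unequal length is handled.

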7.2.5 Parent/Caregiver and Child Unscheduled/Missed Visit

Unscheduled visits for parent/caregiver and child may occur if an enrolled child could not complete the oral health portion during the WCV. But, this is unlikely to happen due to the short amount time required for the oral health activities. Another possibility would be if a child is scheduled by the practice for a well child visit much sooner or later than the visit window. In these cases, study data would be collected per guidelines outlined in the MOP, but the time length between visits will be accounted for in the analysis stage.

Other instances of unscheduled visits at follow-up, i.e. WCV2 or WCV3, may occur if a well child visit is missed by project staff (for example, a child comes in for a sick visit near the time a well child visit is due and the provider completes the well visit also) or another non-participating provider at the practice is scheduled to see the child for a well child visit. In these cases, the ICDAS, A2, A3 and B1 questionnaires will be completed when possible, either in person, by mail or through a link sent via text or e-mail to the parent/caregiver. The B2 follow-up will be completed as planned. In extreme situations, if we have missed the WCV2 or WCV3 and the child is scheduled to come in to see the enrolled provider for follow-up for a problematic issue within 3 months of the missed well child visit, we will arrange to complete the study visit at the follow-up visit. This determination will be made on a case-by-case basis. Arrangements will be made to have the parent/caregiver bring the child to the Dental Research Building for completion of the ICDAS dental screening. Also, due to scheduling irregularities in the part of the parent/caregiver, every child may not be scheduled for an annual WCV. In cases such as this, the parent/caregiver-child dyad may remain enrolled in the study and be seen for completion of 3 consecutive WCV's regardless of their timing. The time length between visits will be accounted for in the analysis stage.

COVID-19 Visits

Visits missed due to the COVID-19 pandemic will follow the protocol outlined above for unscheduled/missed visits.

8 STUDY PROCEDURES / EVALUATIONS

8.1 Study Procedures/Evaluations

The following is a summary of the study procedures and evaluations. Study procedures include interventions, and procedures performed to assess the primary outcome, secondary outcomes, mediators, moderators and confounders. Measures or interventions will occur at the socioecological levels of child, parent/caregiver, provider, and practice. There will also be implementation evaluation at each of these levels except the parent/caregiver. See Table 8.1.1 for more details on the measures, sources, and timeline. According to the timeline of study procedures and evaluations, WCV #1: Baseline Visit = T_0 ; WCV #2: Follow-up Visit = T_3 ; and WCV #3: Final Study Visit = T_6 .

Table 8.1.1 Summary of measures, sources, and timeline

Socioecological levels	Implementation Evaluation	Measures	Score	Source	Timeline
Child	Reach # recruited % attrition Participant characteristics (socio-demographics)	Effectiveness Primary outcome: Dental attendance Secondary outcomes: New caries Oral hygiene Frequency of sweet food & drinks OH-related quality of life Cost	% frequency # of decayed, filled teeth (dft) % freq. tooth brushing % freq. sweet food & drinks ECOHIS overall score Direct dental costs Non-dental direct & dental indirect costs	ICDAS (Pitts, 2004); Medicaid claims ICDAS (Pitts, 2004) NHANES III (CDC) Food Frequency Qx, NHANES 2003-2004 (Dye et al., 2010); YRBS 2017(CDC, 2017) Pahel et al., 2007) Medicaid claims Annotated Cost Qx (Thompson & Wordsworth, 2001)	T ₀ , T ₁ , T ₃ , T ₄ , T ₆ , T ₇ T ₀ , T ₃ , T ₆ T ₀ , T ₃ T ₁ , T ₄ , T ₇
	Confounder: Child medical illness	Overall score	Chi & Rakllos, 2012		T ₀ , T ₃ , T ₆
Parent/ caregiver		Mediators: IPQ-RD Moderators: Socio-demographics Health literacy Social support	Overall & mean construct scores Overall score % categories % mean scores	[name], 2016 (Detroit Dental Health Project, 2004) NHANES III (CDC) Morris et al., 2006 Zimet et al., 1988	T ₀ , T ₁ , T ₃ , T ₄ , T ₆
Provider	Implementation/ Fidelity Observation/ audiotape Parent Exit Qx Adoption & Maintenance % prescriptions + list of dentists given	Mediators: OH knowledge Self-efficacy Confounder: Socio-demographics	% mean scores % categories	Open Wide (NMCOHRC) PACT (AAP) (Lewis et al., 2009)(Quinonez et al., 2014) NHANES III (CDC)	T ₋₁ , T ₂ T ₋₁
Practice	Adoption & Maintenance % complete EMR documentation Practice Qx	Mediators: EMR Documentation Practice readiness, climate, and attitude	% mean scores % mean scores	Stamatakis et al., 2012 Aarons, 2004	T ₄ and T ₆ T ₋₁ , T ₂ ,

T₀ = WCV #1: Baseline Visit (1st intervention)

T₃ = WCV #2: Follow-up Visit (Booster intervention);

T₆ = WCV #3: Final Visit (Follow-up)

T₋₁ = Before WCV #1; T₀ = At WCV #1; T₁ = After WCV #1

T₂ = Before WCV #2; T₃ = At WCV #2; T₄ = After WCV #2 T₅

= Before WCV #3; T₆ = At WCV #3; T₇ = After WCV #3

